## Study Protocol

The Investigators retrospectively analyzed data of all patients treated at our referral Center for moderate to critical AP, as classified by Determinant-Based Classification of Acute Pancreatitis Severity (DBC). Patients treated with interventional or surgical procedures after 4 weeks (late phase) were included in the study, while patients who had undergone conservative treatment, or who has been operated within 4 weeks (early phase) were excluded from the data analysis.

The cohort sample was divided into four groups, according to the first type of the interventional or surgical management performed: percutaneous drainage group (PD), endoscopic approach group (END), surgical internal derivation of WON group (INT), and surgical necrosectomy group (NE). In all cases, the decision to intervene with an invasive procedure was taken on the basis of a clinical course not responsive to conservative management, signs of sepsis due to infected necrosis, or persistent gastric output obstruction with large fluid collections. The operative approach was chosen based on our experience and on the current Literature evidence, using a “tailored” *step-up* approach.

The acute pancreatitis severity was retrospectively graded according to the DBC, based on data drawn from clinical records.

All the procedures had been performed by surgeons, gastroenterologists/endoscopists, or interventional radiologists who composed the multidisciplinary group.

In performing primary PD, catheters up to 16 Fr were inserted using Seldinger technique, guided by ultrasound (US) or Computer Tomography (CT).

In the END approach, a lumen apposing HOT AXIOS™ (Boston Scientific, Boston, MA, USA) 15 x 10 mm metal stent was placed trans-luminally by echo-endoscopic guidance, under conscious sedation. The procedure was completed with the insertion of a naso-cystic catheter to facilitate liquefaction of debris. Further endoscopic sessions and trans-luminal necrosectomy were considered case by case.

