Surgical internal derivation throughout gastric or enteric breach, adopted since 2014, was considered in the case of WON with mature walls. When the WON was not adjacent to the stomach or showed necrosis in its inferior portion, the enteric Roux-en-Y derivation was selected. However, in the vast majority of cases, trans-gastric necrosectomy and internal derivation were carried out. Firstly, a US-guided anterior gastrotomy was performed. Then, large communication up to 80 mm was created between WON and the posterior gastric wall using a mechanical stapler; finally, the necrotic debris was removed from the WON' cavity. At our Center, since 2017, a minimally invasive variant of this

approach has been performed using the da Vinci Xi robot (Intuitive Surgical Inc., Sunnyvale, CA, USA).

The NE was performed either in case of failure of endoscopic/percutaneous drainage or as a first-line treatment. It was accomplished by standard trans-peritoneal laparotomy and continuous post-operative lavage or by retroperitoneal US-guided mini-laparotomic approach, depending on the distribution of the necrotic tissue. When it was applicable, the infra-mesocolic approach was preferred. The standard trans-peritoneal NE was performed in a supine position. The retroperitoneal US-guided mini-laparotomic approach was performed in lateral decubitus: the US-guidance allowed to perform a focused right or left flank mini-laparotomy, and to obtain complete debridement using long instruments, through the retroperitoneal way.

The following variables were evaluated: sex, age, severity of inflammation according to the DBC classification, PA etiology, CT scan severity index according to Balthazar criteria, clinical prognostic score using bedside index of severity of acute pancreatitis (BISAP) score.

Total length of hospitalization, operative management, necrosis cultures, total and post-interventional Intensive Unit Care (ICU) were also recorded and analyzed together with the in-hospital morbidity, mortality and re-admissions.

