Patients were checked after discharge within 14 days and followed monthly as outpatients by gastroenterologists. A CT scan was performed within 4 months, or before in case of recurrent symptoms. During the follow-up, the English Standard Short Form 36 (SF-36) questionnaire was used to evaluate the general quality of life at three and six months, one and two years. The SF-36 examines 8 areas consisting of social and physical function, physical and emotional well-being, bodily pain, vitality, mental health and overall general health perception. At the six-month follow-up, the patients also completed a specific questionnaire about the pancreatic function [10]. In particular, the total score takes in consideration abdominal pain using visual analogue pain score, diarrhea, unintentional weight loss, new onset of diabetes and use of enzyme supplementation. The score ranges between zero to five (all symptoms present).

The work has been reported in line with the STROCCS criteria.

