### *Statistical analysis*

For the data analysis, the Chi-square test was used to define associations between categorical factors and surgical groups. Continuous variables with normal distribution were expressed as mean  $\pm$  standard deviation (SD) and compared using the ANOVA test. Variables with an abnormal distribution were expressed as median and compared using the Kruskal-Wallis Test. A p-value  $\leq 0.05$  was considered

statistically significant. The statistical analysis was performed using SPSS (Statistical Production and Service Solution for Windows, SPSS Inc., Chicago, IL, USA), version 24.

All procedures performed in studies involving human participants were in accordance with the ethical standards of the institutional and/or national research committee and with the 1964 Helsinki declaration and its later amendments or comparable ethical standards. For this type of study, formal consent is not required

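### The quality-of-life and pancreatic-function scores exist only for discharged, living responders, so the planned tests compare survivors of each first procedure, and the plan neither says so nor accounts for the deaths.

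*Protocol*

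**What the plan says.** All references are to the Protocol.

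- **Groups** (section Study Protocol): "The cohort sample was divided into four groups, according to the first type of the interventional or surgical management performed". Membership is therefore fixed at the first procedure. Allocation was by clinical judgement: "The operative approach was chosen based on our experience and on the current Literature evidence".
- **Population** (same section): patients with "moderate to critical AP, as classified by Determinant-Based Classification of Acute Pancreatitis Severity (DBC"), so deaths are plausible.
- **Mortality** (same section): hospital stay, intensive care and related variables "were also recorded and analyzed together with the in-hospital morbidity, mortality and re-admissions". No rate is given, overall or by group. The phrase reads most naturally as mortality in hospital.
- **Follow-up** (same section): "Patients were checked after discharge within 14 days and followed monthly as outpatients by gastroenterologists". Within this follow-up the SF-36 "questionnaire was used to evaluate the general quality of life at three and six months, one and two years". In addition, "At the six-month follow-up, the patients also completed a specific questionnaire about the pancreatic function", scored from zero to five, with five meaning that all symptoms are present.
- **Tests** (section Statistical analysis): "Continuous variables with normal distribution were expressed as mean" and SD and compared by ANOVA; non-normal variables are given as medians and compared by Kruskal-Wallis. The SF-36 is not named there, and nothing is said about patients who died before a visit.

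**The concern.** The groups are defined when the first procedure is done, but the scores can come only from patients who left hospital alive, were still alive at the visit and returned a form. A patient who died in hospital never enters follow-up, and one who died later contributes nothing after that. Both named tests work on the values present, so each group's mean or median describes its survivors.

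If the groups lose different proportions of patients, and those lost are the frailer ones, the surviving sets are not comparable even if the groups were comparable at the procedure. Selection alone then lifts the average of the group with more deaths. What is at stake is a statement about long-term quality of life or pancreatic function after each procedure that a reader takes to cover everyone who had it, when it covers only those who lived to answer.

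**Working it through.** The protocol states no mortality, SF-36 mean, SD or sample size, so there is no figure of its own to reproduce. The calculation below only illustrates size under stated assumptions.

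**Assumptions (none from the protocol).**
- Two groups have the same underlying SF-36 distribution, normal with mean 60 and SD 20; a higher score is better.
- A proportion p of a group dies before the visit. The dead are those at the frail end of a standard normal frailty variable that correlates ρ with the score.
- All survivors respond.

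**Formula.** The survivors' mean exceeds the underlying mean by ρ × SD × g(p), where g(p) = φ(z_p)/(1 − p), φ is the standard normal density and z_p its p-quantile.

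- g(0.05) = 0.1031/0.95 = 0.109
- g(0.10) = 0.1755/0.90 = 0.195
- g(0.20) = 0.2800/0.80 = 0.350
- g(0.30) = 0.3477/0.70 = 0.497

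With ρ = 0.5, ρ × SD = 10, so the survivors' means at 5%, 20% and 30% mortality are 61.1, 63.5 and 65.0.

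**Artefact between two groups** = ρ × 20 × [g(p₂) − g(p₁)], in SF-36 points, in favour of the group with more deaths:

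| Mortality | g(p₂) − g(p₁) | ρ = 0 | ρ = 0.3 | ρ = 0.5 | ρ = 1 |
|---|---|---|---|---|---|
| 5% vs 5% | 0 | 0 | 0 | 0 | 0 |
| 5% vs 10% | 0.086 | 0 | 0.5 | 0.9 | 1.7 |
| 5% vs 20% | 0.241 | 0 | 1.4 | 2.4 | 4.8 |
| 5% vs 30% | 0.388 | 0 | 2.3 | 3.9 | 7.8 |

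The artefact vanishes if mortality is equal (with the same ρ in both groups) or if death is unrelated to the score. The ρ = 1 column is an extreme bound, in which the dead are exactly the lowest scorers.

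**Adding confounding.** Suppose the group with more deaths also began sicker, with an underlying mean d points lower. The survivor difference in its favour becomes the artefact minus d. At 5% versus 20% and ρ = 0.5 this is 2.4 − d: any d above 2.4 makes that group look worse, and a negative d makes the apparent advantage larger. The protocol gives nothing from which to fix d.

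**The case against.** **This is silence that an analysis plan could fill.** Handling of deaths is often left to the SAP, and the Statistical analysis section never mentions the SF-36 or survivors. This stands in part: that the scores are compared between groups, and among survivors only, is inferred from collection after discharge together with the only rule given for continuous variables. But the protocol does name its tests, and as written they leave the dead out.

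**Mortality is reported anyway, and quality of life among survivors is a legitimate question.** Both are true, and they are why the survivor comparison can stay. A separate mortality result does not tell the reader that the quality-of-life comparison is conditional on survival, or on how many patients it rests in each group.

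**The more lethal procedure need not look better.** A reader might infer that the plan will show better quality of life for whichever procedure has more deaths. The documents do not support that. Procedures were chosen case by case, so a group with more deaths may have started sicker and its survivors may still score worse. Only the selection component has a known direction.

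**The sizes are assumed.** This stands. No mortality by group is given, and for a small gap such as 5% versus 10% the artefact is under 1 point at ρ = 0.5.

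**Ranking deaths worst should not replace the survivor comparison.** This also stands. With four SF-36 visits and the six-month score, the same early deaths would enter five comparisons on top of the mortality analysis. A difference labelled quality of life could then come from mortality alone.

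**Conclusion.** The point holds as a conditional one and should be acted on. Followed as written, the plan compares survivors of each first procedure on the SF-36 and the six-month score, without saying so. If mortality differs between groups and is related to frailty, selection biases that comparison towards the group with more deaths. Under the assumed SD of 20, the artefact ranges from nothing at equal mortality to 3.9 points at 5% versus 30% with correlation 0.5, and to 7.8 points at the extreme of correlation 1. These sizes rest wholly on assumed mortality, SD and correlation, and on equal underlying distributions in the groups.

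The documents do not show that mortality did differ, that a bias occurred, or which way the net error would run once the non-random choice of procedure is counted.

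**What to change.** 1. Keep the survivor comparison, but label it, and every conclusion drawn from it, as applying to patients alive at that visit.
2. For each group, at each SF-36 visit and for the six-month questionnaire, report the numbers dead, alive without a form, and responding. Show vital status unknown separately if it occurs.
3. Add a sensitivity analysis at each of these time points: Kruskal-Wallis with known deaths before the visit sharing one tied rank worse than any observed score. For the pancreatic-function score the worst end is the top, so deaths rank beyond five. Count in-hospital deaths, plus later deaths where follow-up records show them, and read the result beside the mortality analysis.

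**Cost.** No new patients or measurements are needed, and the test is one the protocol already uses. In-hospital deaths are on record. Nothing in the protocol says that deaths after discharge were ascertained up to two years, so they may need a search of the outpatient records and some may be missed.

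**Downside.** The ranked result has no SF-36 unit, can be driven by mortality alone, and does not correct confounding by indication. That is why it belongs in a sensitivity analysis.

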### *Statistical analysis*

For the data analysis, the Chi-square test was used to define associations between categorical factors and surgical groups. Continuous variables with normal distribution were expressed as mean  $\pm$  standard deviation (SD) and compared using the ANOVA test. Variables with an abnormal distribution were expressed as median and compared using the Kruskal-Wallis Test. A p-value  $\leq 0.05$  was considered

statistically significant. The statistical analysis was performed using SPSS (Statistical Production and Service Solution for Windows, SPSS Inc., Chicago, IL, USA), version 24.

All procedures performed in studies involving human participants were in accordance with the ethical standards of the institutional and/or national research committee and with the 1964 Helsinki declaration and its later amendments or comparable ethical standards. For this type of study, formal consent is not required

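### The four groups were formed by clinical choice of first procedure, but the stated outcome tests are all unadjusted, so a significant group difference cannot be separated from case mix

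*Protocol*

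**What the plan says.** The Study Protocol section divides the cohort into percutaneous drainage (PD), endoscopic (END), surgical internal derivation (INT) and surgical necrosectomy (NE) groups, "according to the first type of the interventional or surgical management performed". On how that procedure was picked it says: "The operative approach was chosen based on our experience and on the current Literature evidence", within a tailored step-up strategy. INT is the only group given both an anatomical condition and a start year: it was "adopted since 2014, was considered in the case of WON with mature walls".

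The same section lists sex, age, Determinant-Based Classification (DBC) grade, etiology, CT severity index and BISAP as variables evaluated. It lists length of stay, ICU stay, in-hospital morbidity, mortality and re-admissions as recorded and analysed.

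The Statistical analysis section then names the methods: "the Chi-square test was used to define associations between categorical factors and surgical groups", ANOVA for normally distributed variables and Kruskal-Wallis for the others, with p ≤ 0.05 as the threshold, in SPSS version 24. It mentions no regression, stratification, matching or propensity score. It does not say that the group comparisons are descriptive.

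**The concern.** A team that picks the procedure for each patient will tend to send different patients to different procedures. If the features that drive the choice also drive the outcome, the raw groups differ in outcome even when the procedures are equally good. Chi-square, ANOVA and Kruskal-Wallis on raw groups test only whether the groups differ; they cannot say why.

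Tabulating severity and age by group can reveal an imbalance, but does not remove it from the outcome comparison. With a significance threshold declared and no caution attached, a small p-value for death or morbidity across procedure groups is easily read as evidence about the procedures.

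**Working it through.** **1. Reading the text.** Allocation by judgement is stated in the Study Protocol section. Only unadjusted tests are stated in the Statistical analysis section. Morbidity, mortality and re-admission are categorical outcomes said to be analysed, and Chi-square is the only categorical method given. The point rests on these statements. There is no planned figure to reproduce, because the protocol gives no sample size, event rate or effect size.

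**2. Illustration: inputs, all assumed.** Group shares PD/END/INT/NE are 35/25/20/20%. Mortality by DBC moderate/severe/critical is 2/10/35%; morbidity is 25/45/70%. The procedure has no effect. DBC mix (%) is:

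| Mix | PD | END | INT | NE |
|---|---|---|---|---|
| Equal | 40/42/18 | 40/42/18 | 40/42/18 | 40/42/18 |
| Mild | 38/42/20 | 45/40/15 | 52/38/10 | 32/43/25 |
| Strong | 25/45/30 | 50/40/10 | 60/35/5 | 20/45/35 |

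**3. Spurious odds ratio, NE v INT.** Group risk = sum of (DBC share × risk). For strong mix and mortality:
- INT: 0.60×0.02 + 0.35×0.10 + 0.05×0.35 = 0.0645
- NE: 0.20×0.02 + 0.45×0.10 + 0.35×0.35 = 0.1715
- OR = (0.1715/0.8285) / (0.0645/0.9355) = 3.0

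**4. Rejection rate of the crude 4×2 Chi-square test** (4,000 simulated studies per setting):

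| Outcome, mix | OR NE v INT | N=60 | N=100 | N=200 |
|---|---|---|---|---|
| Mortality, equal | 1.0 | 4.7% | 5.3% | 4.6% |
| Mortality, mild | 1.7 | 4.3% | 6.3% | 8.7% |
| Mortality, strong | 3.0 | 8.3% | 13.9% | 29.4% |
| Morbidity, equal | 1.0 | 4.5% | 5.0% | 4.8% |
| Morbidity, mild | 1.4 | 6.5% | 6.6% | 9.0% |
| Morbidity, strong | 1.9 | 11.1% | 14.7% | 29.1% |

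Repeat simulation put the top of the range at about 31%. Stratifying by DBC (generalised Cochran-Mantel-Haenszel) gave 3.6% to 5.2% in all 18 settings, and 3.2% to 5.4% on repetition. That success is built in, because DBC is the only cause of outcome in this model.

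A second model used one binary severity factor, 40 patients per group and event risk 10% or 40%. It gave 4.6%, 7.7%, 19.5% and 47.3% as imbalance rose from none to extreme.

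**5. Calendar period, only if accrual began before 2014.** Suppose half of the non-INT patients predate 2014 and that period carries an OR of 2. The crude NE v INT mortality OR is then 1.4/2.4/4.1 (equal/mild/strong). Adjusting for DBC alone leaves 1.45 to 1.47; adding period, or restricting to patients since 2014, gives 1.0.

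**6. Price of adjustment**, strong mix, N=100. Fold width of the NE v INT 95% interval (upper limit over lower) = exp(2 × 1.96 × SE). Expected NE deaths are 20×0.1715 = 3.43 and INT deaths 20×0.0645 = 1.29. The crude SE is √(1/3.43 + 1/16.57 + 1/1.29 + 1/18.71) = 1.087, and exp(3.92×1.087) ≈ 71. The other SEs come from the expected information of the logistic model:

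| Model | Mortality SE (fold width) | Morbidity SE (fold width) |
|---|---|---|
| Crude | 1.087 (71) | 0.650 (13) |
| DBC | 1.198 (109) | 0.712 (16) |
| DBC + period | 1.248 (133) | 0.751 (19) |
| DBC, since 2014 only | 1.387 (230) | 0.874 (31) |

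Expected events are 12.3 deaths and 42.8 morbidity events. With 3 group, 2 DBC and 1 age parameter, that is 12.3/6 ≈ 2.0 and 42.8/6 ≈ 7.1 events per parameter. Under the since-2014 restriction (60 patients, 6.8 deaths, 24.8 morbidity events) it is 1.1 and 4.1. The chance of no INT death at all is (1 − 0.0645)^20 = 0.26.

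**The case against.** The strongest reply is that nothing is misstated. The wording about associations is descriptive, the tests suit that purpose, and no comparative-efficacy objective or recommendation appears. This stands in part: the fault lies in the missing caution and in a threshold attached to comparisons that cannot be interpreted causally, not in a false claim.

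A second reply is that covariate models belong in a statistical analysis plan that may exist unseen. This carries less weight. The protocol has its own statistical section, written in the past tense, naming the tests and the software. The point is about that stated choice.

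A third is that the cohort is already homogeneous. Entry is restricted by severity and timing: "Patients treated with interventional or surgical procedures after 4 weeks (late phase) were included in the study". The indications were also shared: "In all cases, the decision to intervene with an invasive procedure was taken on the basis of a clinical course" that had not responded to conservative care, or for the other listed reasons. This narrows case mix, but it governs whether to intervene, not which of four procedures to use.

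A fourth is that the numbers are invented and adjustment works only because the model was built so. This is correct. No wall-maturity effect was included, although mature walls are the stated anatomical condition for INT. The benefit shown is a best case.

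A fifth concerns the severity variable: "The acute pancreatitis severity was retrospectively graded according to the DBC, based on data drawn from clinical records", with no time point. If the grade reflects the whole course, adjusting for it could condition on events after the procedure and add bias. This stands and limits the fix.

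Two stronger readings are tempting but unsupported. A reader might infer that NE is loaded with failed drainages, since necrosectomy was also done after failure. Grouping follows the first procedure, so those patients stay in PD or END. A reader might also infer that INT is necessarily compared with older controls. No inclusion dates are given, so that holds only if some patients were treated before 2014.

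**Conclusion.** The concern holds as a limit on interpretation. Groups were formed by judgement, the stated tests are unadjusted, and no caution is given, so a significant outcome difference cannot be attributed to procedure rather than case mix. That conclusion rests on the text alone, with high confidence.

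Its size cannot be established. On the assumed inputs it runs from nil (equal mix), through close to nominal (mild mix, about 4% to 9% rejection), to substantial (strong mix, 8% to 29%). These figures show what could happen. They are not evidence that the groups differ or that any result is biased, and a reader who infers that goes beyond the document.

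This should be fixed because the minimum remedy is cheap. It does not make the data unusable.

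**What to change.** 1. In the Statistical analysis section, label the unadjusted group comparisons descriptive, draw no conclusion on relative efficacy from them, and state that residual confounding by wall maturity, collection location and indication remains. Keep mortality descriptive if deaths are few. This costs a few sentences.

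2. For continuous outcomes, and for binary outcomes with enough events, add a comparison adjusted for a small set of recorded covariates that predate the first procedure: age plus one of DBC, CT index or BISAP. Penalised (Firth) logistic regression suits binary outcomes, and a linear or rank-based model suits continuous ones, with 95% confidence intervals. Use DBC only if it can be fixed as of before the first procedure. If covariates were chosen after data collection, say so.

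3. Report procedure dates by group. Only if some patients were treated before 2014, add a period term or a since-2014 sensitivity analysis for comparisons with INT.

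Steps 2 and 3 widen intervals, leave few events per parameter, may require severity to be abstracted again at a pre-procedure time point, and need a check that SPSS 24 can fit the chosen model. They do not remove unmeasured confounding, so step 1 is needed whether or not they are done.
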